8.2 Subject Randomization

Following the safety run-in period in Part 1, subjects will be randomly assigned to Treatment Arms A or C in Part 2 with a 1:1 ratio, adaptively, until reaching the desired number of subjects assigned in each arm. For details please refer to [Section 5.1.4](#).

8.3 Populations for Analysis

The following subject populations will be evaluated and used for presentation and analysis of the data:

- Safety Population: All subjects who received at least 1 dose of study drug (INXN-1001, INXN-2001, and/or palifosfamide).

- Efficacy Evaluable Population: All subjects who received at least 1 dose of study drug (INXN-1001, INXN-2001, with or without palifosfamide) and have at least 1 post-screening response evaluation.

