1 Safety Run-in	A	Ad-RTS-hIL-12 monotherapy; n=6 [INXN-1001 (140 mg daily) + INXN-2001 (███████████)]
	C	Combination therapy; n=3 [INXN-1001 (140 mg daily) + INXN-2001 ██████████ ██████████ + palifosfamide (120 mg/m ²)]
2 Randomization	A	Ad-RTS-hIL-12 monotherapy [INXN-1001 (140 mg daily) + INXN-2001 ██████████ 10 ¹² vp)]
	C	Combination therapy [INXN-1001 (140 mg daily) + INXN-2001 ██████████ ██████████ + palifosfamide (120 mg/m ²)]

	
treatment, then this treatment arm will be included in Part 2 of the study.
 
During Part 2, 9 additional subjects will be randomly assigned to Arm C. If <6 of the first 12 (3+9) subjects survive progression-free at week 16, no additional subjects will be enrolled. If ≥ 6 of the 12 subjects survive progression-free at week 16, an additional 14 subjects will be randomly assigned. If ≥ 15 of the 26 (3 + 9 + 14) subjects in the expansion cohort survive progression-free at week 16, then this regimen would be considered worthy of further investigation (ie, a confirmatory trial).
 
The primary efficacy endpoint is the 16-week PFS rate, defined as the proportion of subjects that remain progression-free at week 16 by mRECIST v1.1 for Arms A and C. Futility decisions will be made using results at week 16 from both primary and secondary endpoints.
 
The safety of study treatments will be assessed throughout the study by the frequency and severity of adverse events (AEs) as determined by the National Cancer Institute (NCI) Common Terminology Criteria for Adverse Events (CTCAE) v4.03.
 
An SRC meeting can be convened if deemed necessary by the sponsor or the investigators at any point during the study.

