- 23. A Follow-Up Tumor Assessment visit will be performed 35 ± 7 days after the Post-Treatment Safety Assessment visit. This assessment is required for all subjects, including those with prior objective evidence of disease progression to ensure that more slowly declining tumor burden in response to therapy is not missed.

NOTE: Subjects without objective evidence of disease progression should continue to have tumor assessments performed at 8 to 10-week intervals until disease progression has been confirmed or an alternate anticancer therapy has been initiated, whichever occurs first.
- 24. Interim cancer history information will include documentation of any new concomitant medications and any anticancer treatments received since the Post-Treatment Safety Assessment visit or the previous tumor assessment.

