6.4.3 Efficacy Assessments

Appropriate cancer staging procedures should be performed during screening. For the purpose of this clinical trial, the following imaging is expected at screening:

- a. CT of the chest, and CT (or MRI) of the abdomen
- b. MRI (or CT) of the brain if brain metastasis are known or suspected

c. CT or MRI of other anatomical regions as clinically indicated

For each subject, disease sites are to be assessed throughout the study using the same method(s) of assessment used at screening. Chest and abdomen imaging are required for all follow-up imaging time points; images of the brain and other anatomical regions should be acquired on follow-up if positive at screening and as clinically indicated.

Target and non-target lesions should be selected and measured as per mRECIST v1.1 guidelines³⁹ (see [Appendix 4](#)). Lesions that will be/are injected with INXN-2001 and/or biopsied should not be selected as target lesions, but should be assessed as non-target lesions. For each subject, disease sites are to be assessed throughout the study using the same method(s) of assessment used at screening. Tumor response assessments will occur at 12 weeks, 16 weeks, and the Follow-up Tumor Assessment visit (24 weeks) for all subjects, including those who may have experienced a dose delay. Additional tumor response assessments may occur at the discretion of the investigator.

The investigator will evaluate each subject for response to therapy according to mRECIST v1.1 guidelines.

In the setting of this immunotherapy, a progression observed \leq week 12 requires confirmation at week 16 (see [Appendix 4](#) for further details). Subjects without objective evidence of disease progression at the Follow-Up Tumor Assessment visit should continue to have tumor assessments performed at 8-10 week intervals until disease progression has been documented, or an alternate anticancer therapy has been initiated, or up to 1 year, whichever occurs first.

In addition to radiological imaging techniques, photographs of visible cutaneous lesions should also be obtained. Digital photograph(s) with included measuring tape should be taken of all visible injected and non-injected tumors, and of any remaining visible local reactions in or around the injected lesion(s). Important guidelines regarding photographic methodology will be provided in a separate manual.

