8.4 Study Endpoints

8.4.1 Primary Efficacy Endpoint

The primary efficacy endpoint is the 16-week PFS rate, calculated as the number of subjects who had not progressed or died prior to 16 weeks from the date of their first dose, divided by the number of subjects in the study arm. Subjects who neither progressed nor died, but had their last tumor assessment prior to 16 weeks, will not be categorized as progression-free and will not be included in the numerator. Progressive disease (PD) will be determined by mRECIST v1.1 (please refer to [Appendix 4](#)).

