8.6.4 Efficacy Analyses

The Efficacy Evaluable Population will be used for the analyses of efficacy data by study arm.

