8.6.4.1 Primary Efficacy Analyses

The primary analysis of the primary endpoint (16-week PFS rate) will be summarized using both a point estimate and its exact binomial 2-sided 95% confidence interval (CI). The 16-week PFS rate will be also estimated using the Kaplan-Meier method. The 95% CI of the PFS rate at 16 weeks will be calculated using the Greenwood formula.

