8.6.4.2 Secondary and Other Analyses

PFS is defined per subject as the time (in months) from first dosing date to the date of progression. Subjects who died without a reported prior progression will be considered to have progressed on their date of death. Subjects who did not progress or die will be censored on the date of their last tumor assessment. Duration of response will be computed from the time measurement criteria were met for PR or CR until the date of documented PD or 1 year. Subjects who neither progressed nor died will be censored on the date of last tumor assessment.

INXN-1001 PK parameters to be determined will include, but are not limited to, the maximum concentration (C_{max}), time to maximum concentration (T_{max}), half-life ($t_{1/2}$), area-under-the-concentration time curve (AUC), volume of distribution (V_d), and clearance (CL). Where possible, descriptive statistics of the PK parameters will be provided; individual subject INXN-1001 concentrations, actual sampling times, and PK parameters will be listed.

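### The primary 16-week PFS rate has one denominator in Protocol 8.4.1 and another in 8.3/8.6.4; following the latter drops dosed failures who were never scanned and can only raise the reported rate

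*Protocol*

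**What the plan says.** Protocol 8.4.1 defines the primary rate as the number of subjects who had neither progressed nor died before 16 weeks from first dose, "divided by the number of subjects in the study arm". Subjects without an event whose last tumor assessment came before week 16 are kept out of the numerator, which makes them failures.

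Protocol 8.6.4 states: "The Efficacy Evaluable Population will be used for the analyses of efficacy data by study arm". Section 8.3 requires members of that population to have received study drug "and have at least 1 post-screening response evaluation". The primary analysis in 8.6.4.1 sits under 8.6.4. It says that the rate "will be summarized using both a point estimate and its exact binomial 2-sided 95% confidence interval (CI"), with a Kaplan-Meier estimate as well, and names no other population.

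On deaths, 8.6.4.2 says: "Subjects who died without a reported prior progression will be considered to have progressed on their date of death".

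On scan timing, 6.4.3 says: "Tumor response assessments will occur at 12 weeks, 16 weeks, and the Follow-up Tumor Assessment visit (24 weeks) for all subjects". Footnote 23 to Tables 2A and 2B adds, for the follow-up scan: "This assessment is required for all subjects, including those with prior objective evidence of disease progression".

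The synopsis decision rules are fixed counts. Arm A needs at least 1 of the first 6, then 3 of 13, then 9 of 33. Arm C needs at least 6 "of the first 12 (3+9) subjects survive progression-free at week 16", then 15 of 26. Sections 4.1.5 and 5.4 allow a subject to be added when another stops before 6 cycles for a reason other than progression. Section 8.1 describes the stage sizes as subjects evaluated.

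**The concern.** The two rules treat the same dosed subject differently. Someone who dies, withdraws or misses imaging before any post-screening scan stays in the denominator as a failure under 8.4.1 and disappears under 8.3 and 8.6.4. Every dosed subject removed in this way is a failure under 8.4.1, so the direction of the bias is known in advance: upward.

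Nothing supplied settles which rule governs. Protocol 8.8 defers detail to a formal plan. The supplied SAP describes a single-arm, single-center Phase Ib/II study with 12-week endpoints and its own populations (SAP 5.2 and 6.2), so it does not help. In an open-label trial, an unresolved denominator can be chosen after outcomes are known.

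At stake is the headline efficacy estimate in each arm and, in small arms, whether its confidence interval appears to exclude the rate of no interest.

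**Working it through.** **1. Who differs between the denominators**

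| Subject | 8.4.1 | 8.3 with 8.6.4 |
|---|---|---|
| Dosed, scanned at least once, progression or death before week 16 | failure | failure |
| Dosed, scanned at least once, no event, last scan before week 16 | failure | failure |
| Dosed, dies or leaves before any scan | failure | excluded |
| Randomised in Part 2, never dosed | unclear; possibly in the denominator | excluded |

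The third row is the substance of the point. On the fourth, the words about subjects in the arm could include the undosed, but 8.4.1 measures time from first dose, which favours a dosed denominator.

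**2. The plan's own figures**

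Inputs from 8.1 and the synopsis: Arm A p0 = 0.15, p1 = 0.35, continue at 3 or more of 13, go at 9 or more of 33. Arm C p0 = 0.40, p1 = 0.65, continue at 6 or more of 12, go at 15 or more of 26.

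P(go) = sum, over stage 1 counts x at or above the continue threshold, of P(X1 = x) × P(X2 ≥ r − x), where r is the go count.

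- Arm A: error 4.1%, power 80.8%. Adding the synopsis look at the first 6 subjects gives an error of 3.9%.
- Arm C: error 4.7%, power 80.9%.

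These reproduce the stated 80% power within a one-sided 5% limit. They require fixed denominators of 13/33 and 12/26.

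**3. Effect on the reported rate**

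With x successes, N dosed and k dosed but unscanned, the rate is x/N under 8.4.1 and x/(N − k) under 8.6.4. Intervals are exact 95%. The documents give no value of k, so each k is an assumption.

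| Arm | k | Rate | 95% CI | Shift (points) |
|---|---|---|---|---|
| A | 0 | 9/33 = 27.3% | 13.3–45.5 | – |
| A | 1 | 9/32 = 28.1% | 13.7–46.7 | +0.9 |
| A | 4 | 9/29 = 31.0% | 15.3–50.8 | +3.8 |
| C | 0 | 15/26 = 57.7% | 36.9–76.6 | – |
| C | 1 | 15/25 = 60.0% | 38.7–78.9 | +2.3 |
| C | 2 | 15/24 = 62.5% | 40.6–81.2 | +4.8 |

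At k = 4 in Arm A and k = 2 in Arm C, the lower limit moves above the rate of no interest (15% and 40%).

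**4. Effect on the decision rule**

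The rules count successes against fixed thresholds. Dropping an unscanned failure without replacement adds no success, so it cannot create a go.

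Inflation needs two further conditions: unscanned failures are both excluded and replaced, and 15% and 40% are null rates among all dosed subjects. If a fraction d is unscanned and replacement is unlimited, the null rate among those counted is p0/(1 − d). At d = 5% (assumed), this is 0.15/0.95 = 0.158 and 0.40/0.95 = 0.421. The error is then 5.1% in Arm A (with the first-6 look) and 7.3% in Arm C, against 3.9% and 4.7%. This is an upper bound, because additions are allowed only after discontinuation for reasons other than progression.

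**The case against.** The two sections can be read together: 8.4.1 gives the formula, 8.6.4 gives the population, and the result is evaluable subjects in the study arm. On that reading 8.4.1 still has work to do for subjects scanned at least once. This stands as a possible reading, but the text does not state it, and it would remove deaths before any scan, which 8.4.1 counts as failures.

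This study's own statistical plan may settle the matter. That also stands; the statement that nothing resolves it applies only to the documents supplied.

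Few subjects should be unscanned. Scans are required for all, including after dose delay, and the follow-up scan is required even after progression. Those provisions keep many early stoppers evaluable, though they cannot recover deaths or withdrawals of consent. The shifts above, at most 4.8 points, are also small beside intervals roughly 32 to 41 points wide.

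A reader might infer that the conflict inflates the false-go rate beyond 5%. The documents do not support that. Sections 4.1.5 and 5.4 speak of adding a subject, not of removing the earlier one, and the synopsis rules are written on enrolled counts. If 15% and 40% are instead null rates among evaluated subjects, as the wording of 8.1 allows, replacement leaves the error at 3.9% and 4.7%. The heading of 5.4 and that same wording leave some ambiguity, which justifies a clarifying sentence and no more.

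**Conclusion.** The inconsistency is real and bears on the primary endpoint. For dosed subjects its direction is certain: applying 8.6.4 can only raise the reported 16-week PFS rate. Its size is not known, because it depends on how many dosed subjects have no post-screening scan. The illustrations of +3.8 points (Arm A, 4 unscanned) and +4.8 points (Arm C, 2 unscanned) rest on assumed numbers at the minimum go counts.

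As written, the go/no-go error is not shown to be inflated. The 5.1% and 7.3% figures are a conditional upper bound and do not support the severity. It would also go too far to say that the denominators differ only for dosed subjects, since those randomised but never dosed are not clearly placed. Severity: minor to moderate.

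**What to change.** In 8.3 and 8.6.4, state that the primary 16-week PFS rate and the Simon counts use all dosed subjects by arm, with death, withdrawal or no week-16 assessment counted as not progression-free, as in 8.4.1. Say explicitly that this reads the 8.4.1 denominator as dosed subjects, and report randomised-but-undosed subjects separately. Keep the Efficacy Evaluable Population as a sensitivity analysis.

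In 4.1.5, 5.4 and 8.1, state that an added subject does not displace a dosed subject from the 6/13/33 (Arm A) or 12/26 (Arm C) counts.

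The cost is wording only, with no extra subjects or visits. The reported rate may be slightly lower, and losses unrelated to disease will count as failures; the sensitivity analysis shows how much that matters.

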8.4 Study Endpoints

8.4.1 Primary Efficacy Endpoint

The primary efficacy endpoint is the 16-week PFS rate, calculated as the number of subjects who had not progressed or died prior to 16 weeks from the date of their first dose, divided by the number of subjects in the study arm. Subjects who neither progressed nor died, but had their last tumor assessment prior to 16 weeks, will not be categorized as progression-free and will not be included in the numerator. Progressive disease (PD) will be determined by mRECIST v1.1 (please refer to [Appendix 4](#)).

8.4.2 Secondary Efficacy Endpoints

Tumor-related secondary efficacy endpoints are defined as the following:

- PFS: time from the date of first dose to the date of PD or death (if prior to progression). Subjects without PD or death occurring as of the time of analysis will be censored as of the last date of disease evaluation. PD will be evaluated by mRECIST v1.1
- ORR by mRECIST v1.1: Proportion of subjects achieving a confirmed PR or CR according to mRECIST v1.1 during study. All objective responses (CR or PR) require confirmation by a repeat tumor assessment at least 4 weeks (28 days) after the response is first observed in order for the response to be considered confirmed.
- Duration of response: time from the date of first objective response (PR or CR) by mRECIST v1.1, until the date of PD or 1 year. Duration of response in subjects who have not progressed or died at the time of analysis will be censored as of the date of their last tumor assessment.
- Clinical benefit rate (CBR = proportion of subjects with CR, PR or SD) by mRECIST v1.1

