14. Centralized registration of eligible subjects will be completed according to a process defined by the Sponsor. During Part 1 of the study, subjects will be registered by the Medical Monitor to one of the treatment arms; during Part 2, subjects will be randomly assigned to a treatment arm.
15. Appropriate cancer staging procedures should be performed during screening. For the purpose of this clinical trial, the following imaging is expected at screening:
 - a. CT of the chest, and CT (or MRI) of the abdomen
 - b. MRI (or CT) of the brain, if brain metastasis are known or suspected
 - c. CT or MRI of other anatomical regions as clinically indicated

All imaging should be of diagnostic quality and include IV contrast. PET imaging is an acceptable alternative modality provided the CT component is of diagnostic quality as per RECIST 1.1 guidelines.

For subjects with measurable lesions, target lesions should be selected and measured as per mRECIST v1.1 guidelines. ([Appendix 4](#)) Lesions that will be/are injected with INXN-2001 and/or biopsied should not be selected as target lesions, but should be assessed qualitatively as non-target lesions.

Disease sites are to be imaged throughout the study using the same method(s) used at screening. Chest and abdomen imaging are required for all follow-up imaging time points; images of the brain and other anatomical regions should be acquired on follow-up if positive at screening and as clinically indicated.

Tumor response assessments will occur at 12 weeks and 16 weeks (C5D1 and C6D7), and the Follow-up Tumor Assessment visit (24 weeks) for all subjects, including those who may have experienced a dose delay. In the setting of this immunotherapy, a progression observed at week 12 requires confirmation at week 16. Additional tumor response assessments may occur at the discretion of the investigator.

16. A blood sample(s) for cytokine profiling, breast cancer-associated biomarker levels (eg, MUC-1), and also INXN-1001 levels. Please refer to the Laboratory Manual for details regarding sample processing and shipment.

Screening (post-registration)

Cycle 1 - Days 2, 3, 7, and 15

Cycle 3 - Days 2, 3, 7, and 15

[figure not shown]
Cycle 5 - Day 1 (to coincide with the tumor assessment)

Cycle 6 - Days 2, 3, 7, and 15

Post-treatment Safety Assessment

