17. Digital photograph(s) of all visible injected and non-injected tumor(s), and of any visible local reactions in or around the injected lesion(s). Photographs are required post-registration, Cycle 2 Day 7, Cycle 5 Day 1, Cycle 6 Day 7, Post-Treatment Safety Assessment, and Follow-Up Treatment Assessment visits, and ad hoc as the investigator deems necessary. Important guidelines regarding photographic methodology will be provided in a separate manual.
18. Intratumoral INXN-2001 [REDACTED] injection should be administered 3 hours \pm 30 minutes after the INXN-1001 dose. [REDACTED]
[REDACTED] Each subject will be carefully monitored for possible local reactions at the injection site and/or hypersensitivity reactions for at least 2 hours following the INXN-2001 injection. A detailed description of physical location(s) of the injected tumor(s) and surrounding tissue, and any visible local reactions will be documented. The [REDACTED]

19. The subjects will be dispensed INXN-1001 for self-administration after Day 1. The first INXN-1001 dose will be given at the clinical site in a fed state (within approximately 30 minutes after the start of a normal meal). The remaining 6 doses can be self-administered at the same time as on Day 1 (\pm 1 hour) in the fed state. Study sites must verify adherence with INXN-1001 dosing. Subjects should return bottles of INXN-1001 to the clinical site to determine extent of subject adherence to self-administration preferably on Day 7.
20. The following temporal sequences of drug administration for Arm A monotherapy and Arm C combination therapy will be followed:

For subjects enrolled in Arm C Ad-RTS-hIL-12 + palifosfamide Combination Therapy, the sequences for monotherapy + palifosfamide (sequences for Arms A + C) will be followed concurrently as shown above.

21. Day 1 clinical laboratory assessments may be performed within 15 days of the previous cycle through the Day 1 (prior to dosing) clinic visit. Clinical laboratory tests drawn for analysis prior to dosing on Day 15 of each cycle may be used for determining if the re-treatment criteria have been met, and must be reviewed by the investigator or designee prior to the next cycle of study drug administration. Repeat assessments may be obtained for those subjects with parameters \geq Grade 3.

- 22. Post-Treatment Safety Assessment visit will be performed 28 ± 3 days after the last dose of study drug or prior to receiving another anticancer therapy.

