4.1.1 Study Design and Treatment Arm Expansion Procedure

4.1.1.1 Overall Study Design

This is a randomized, open-label, Phase II study of Ad-RTS-hIL-12 monotherapy or Ad-RTS-hIL-12 in combination with palifosfamide in subjects with recurrent/metastatic breast cancer with accessible lesions.

Two treatment arms will be assessed for safety, followed by random assignment to Ad-RTS-hIL-12 monotherapy or combination therapy. Each subject will be treated for up to 6 treatment cycles, with each cycle being 21 days in duration.

Safety and tolerability will be assessed by the incidence and severity of AEs as determined by National Cancer Institute (NCI) Common Terminology Criteria for Adverse Events (CTCAE) v4.03. A SRC comprised of the Medical Monitor, enrolling Principal Investigators (PIs), and Sponsor representatives, will be convened to review safety information and to decide upon further subject enrollment.

The antitumor activity of study treatment will be assessed according to mRECIST v1.1 guidelines.³¹ ([Appendix 4](#))

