5.3 Withdrawal of Subjects from Study Treatment and/or Study

The investigator and/or the subject have the right to terminate the subject's participation in the study at any time. Subjects who discontinue study drug should complete the Post-Treatment Safety Assessment visit.

A subject **may** withdraw (or be withdrawn) from the study treatment prematurely for any of the following reasons:

- PI determines further participation is not in subject's best interest.
- Clinically significant disease progression

NOTE: In the absence of rapid clinical deterioration, disease progression should be confirmed by a repeat, consecutive assessment no less than 4 weeks from the date first documented to ensure that more slowly declining total tumor burden in response to therapy is not missed.

A subject **MUST** be withdrawn in the event of any of the following:

- Withdrawal of informed consent.
Note: Any subject who wishes to withdraw from the study treatment may do so but will be counseled that follow-up for the effects of immunotherapy is strongly recommended.
- Any treatment-related AE meeting withdrawal criteria.
- Substantial noncompliance with the requirements of the study.
- Subjects with a confirmed positive pregnancy test.
- Any intercurrent illness that would, in the judgement of the investigator, affect assessments of clinical status to a significant degree and require discontinuation of protocol therapy.

Every effort should be made to follow subjects who withdraw from study treatment with ongoing treatment-related AEs in order to determine the outcome of the event.

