A missed Day 2 or Day 3 study drug administration may be rescheduled to Day 4 of the same treatment cycle. If both Day 2 and Day 3 are missed, then only a single day may be rescheduled to Day 4 and the other will be skipped. In either case, the total duration of the treatment cycle should remain 21 ± 1 day by shortening the rest interval by 1 day. If the missed dose cannot be administered on Day 4, then it must be skipped and the subject should continue on protocol and take the next dose as originally planned.

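### On the printed schedule the week-12 and week-16 scans are 27 days apart, one day too few for the week-16 scan to confirm a week-12 response for ORR

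*Protocol*

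**What the plan says.** Protocol section 8.4.2 defines ORR as "Proportion of subjects achieving a confirmed PR or CR according to mRECIST v1.1 during study", and says that all objective responses "require confirmation by a repeat tumor assessment at least 4 weeks (28 days) after the response is first observed". The interval is given in days as well as weeks, so it cannot be read as approximate.

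The scan days come from footnote 15 to Tables 2A and 2B: "Tumor response assessments will occur at 12 weeks and 16 weeks (C5D1 and C6D7"). Table 2B marks imaging in the same two cycles. Neither gives a window for the scan. Section 4.1.1.1 describes treatment in cycles, "with each cycle being 21 days in duration".

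Section 6.4.3 gives the schedule in weeks only: "Tumor response assessments will occur at 12 weeks, 16 weeks, and the Follow-up Tumor Assessment visit (24 weeks) for all subjects". Footnote 15 and section 6.4.3 both allow extra assessments at the investigator's discretion.

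The synopsis (Study Design) says that week-16 futility decisions draw on primary and secondary endpoints. Section 8.4.1 counts 16 weeks from first dose, and keeps out of the numerator any event-free subject whose last tumor assessment came before that point.

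The SAP supplied describes a single-arm study with scans at weeks 6 and 12. It does not settle the question.

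**The concern.** The week labels suggest that the two on-treatment scans were meant to be four weeks apart, so that the second could confirm the first. The printed cycle days do not deliver that. If the rule is applied as written, a subject exactly on schedule with a PR at both scans is not a confirmed responder at week 16.

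Two things are at stake. First, ORR is a stated secondary objective, and a response seen at both scans but gone by the next one would be scored as no response. The error runs in one direction only. Second, the week-16 review would see no confirmed responses among on-schedule subjects first found to respond at week 12, whatever the treatment does, unless extra scans had been done.

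**Working it through.** **Inputs.** Cycle length 21 days (section 4.1.1.1). Scans at C5D1 and C6D7 (footnote 15). Minimum confirmation interval 28 days (section 8.4.2). Safety visit 28 ± 3 days after the last dose (footnote 22). Follow-up scan 35 ± 7 days after the safety visit (footnote 23).

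**Study day = (cycle − 1) × 21 + cycle day.**

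- C5D1: 4 × 21 + 1 = study day 85, which is 84 days after first dose. 84 / 7 = 12.0 weeks, so the week-12 label reproduces.
- C6D7: 5 × 21 + 7 = study day 112, which is 111 days after first dose. 111 / 7 = 15.86 weeks, so the week-16 label does not reproduce; it is one day short.
- Gap: 112 − 85 = 27 by study day, and 111 − 84 = 27 by elapsed days. A gap of 28 appears only if elapsed day 84 is set against study day 112.

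**Sensitivity to cycle length.** In the provision for missed Day 2 or Day 3 doses, the protocol says that "the total duration of the treatment cycle should remain 21 ± 1 day". This is not an imaging window, but it shows how fine the margin is. The gap is the length of Cycle 5 plus 6 days: 26, 27 or 28 days for a cycle of 20, 21 or 22 days. Only the longest meets the rule.

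**Next scheduled scan.** Take the last INXN-1001 dose as C6D7, study day 112. The "Post-Treatment Safety Assessment visit will be performed 28 ± 3 days after the last dose of study drug", and the follow-up scan comes after that.

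| | Study day | Days after C5D1 | Days after C6D7 |
|---|---|---|---|
| Earliest: 112 + 25 + 28 | 165 | 80 | 53 |
| Nominal: 112 + 28 + 35 | 175 | 90 | 63 |
| Latest: 112 + 31 + 42 | 185 | 100 | 73 |

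This scan meets the 28-day rule, so a response that lasts until then is confirmed.

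**Primary endpoint.** Sixteen weeks is 112 days after first dose, which is study day 113 (C6D8). C6D7 falls one day before it. Read literally, section 8.4.1 would not count as progression-free an event-free subject whose latest scan is C6D7. That is the position of on-schedule subjects when week-16 results are first reviewed.

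**Illustration of the ORR loss.** The documents give no response durations. Assume that responses still present at study day 112 end exponentially, with a median of 91 days (3 months) or 182 days (6 months), and that no extra scan is done. The share lost in the 63 days before study day 175 is 1 − 2^(−63/91) = 38%, or 1 − 2^(−63/182) = 21%. Both durations are assumed, so these figures show scale only.

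**The case against.** The strongest reply is that the mismatch rests on one parenthesis. Section 6.4.3 and the synopsis give weeks alone, and weeks 12 and 16 are exactly 28 days apart. This is right about the source of the error: it is a visit mapping that is one day out. It does not remove the error, because the footnote assigns the visits and no tolerance is stated in either place.

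It can also be said that the response is not lost for good. Section 8.4.2 sets a minimum interval with no upper limit, ORR covers the whole study, and the follow-up scan, later scans or an optional scan can confirm. This stands. A reader might infer that every week-12 responder drops out of ORR, or that 21% to 38% do. The documents support neither. Only subjects whose response ends, or who have no further scan, before a later confirmation are affected.

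Third, ORR is secondary and has no target or threshold, and the Simon stage rules count subjects progression-free at week 16. This also stands: the 28-day rule does not enter those counts. The synopsis nevertheless lets secondary endpoints inform the same decisions, without saying how.

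A reader might also infer that a subject with a dose delay can be confirmed while one on schedule cannot. If the scan moved with a Cycle 6 delayed by 7 or 14 days, the gap would be 34 or 41 days. But footnote 15 and section 6.4.3 keep the scans at weeks 12 and 16 even after a delay, so this would hold only if scans were shown to follow the cycle.

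Lastly, section 5.3 says that "disease progression should be confirmed by a repeat, consecutive assessment no less than 4 weeks from the date first documented". It is tempting to conclude that week-12 progression cannot validly be confirmed at week 16. That section concerns withdrawal from study treatment. For the endpoint, section 6.4.3 and Appendix 4 name week 16 as the confirming visit and set no minimum interval.

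**Conclusion.** The inconsistency is real and exact. The printed scan days are 27 days apart, the rule needs 28, and no window bridges the difference. For subjects on the printed schedule, the week-16 scan cannot confirm a response first seen at week 12.

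The consequence is a downward bias in ORR of unknown size, limited to responses present at both scans but not documented at a later one. A further consequence is that, on scheduled scans, no week-12 response in an on-schedule subject is confirmed at week 16. The same one-day slip puts the scan just before the 16-week point of the primary endpoint.

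This rests on 21-day cycles without delay, scans on the printed days and no extra scan. The follow-up dates also assume that all six cycles are given, with the last dose at C6D7. It should be corrected because a rule applied as written gives an unintended result and the correction is small.

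**What to change.** In footnote 15 and Table 2B, set the week-16 scan at study day 113 (C6D8) or later and at least 28 days after the week-12 scan, with a stated window, for example study days 113 to 119. With that window both conditions can be met if the week-12 scan is no later than study day 91 (119 − 28), so a window for the week-12 scan should be stated too. The imaging row in Appendix 6 should follow.

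This is better than keeping C6D7 and allowing a shorter interval in section 8.4.2. That would repair ORR but leave the scan 111 days after first dose, before the cutoff in section 8.4.1.

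For section 5.3, the sponsor should be asked only to reconcile its four-week wording with footnote 15 and Appendix 4. No replacement wording is proposed, because that section governs withdrawal from treatment.

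The cost is a line in the footnote and matching table entries, with no added scan. The downside is that the scan may fall one or more days after the Day 7 visit.
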